1.2 Purpose

B-cell depleting therapies have in the past been shown to impair the immune response to conventional vaccines. The objective of this study is to assess whether participants treated with monthly s.c. injections of ofatumumab (20 mg) can mount an adequate immune response to the new class of SARS-CoV-2 modRNA vaccines (initial or booster) as measured by humoral and cellular responses. The study will further investigate the maintenance of SARS-CoV-2 specific responses for up to 18 months after the initial vaccination.

2 Objectives and endpoints

Table 2-1 Objectives and related endpoints

Objective(s)	Endpoint(s)
Primary Objective(s) 
 To estimate the proportion of RMS patients having established SARS-CoV-2-specific T cells after receiving a modRNA vaccine (initial vaccination or booster) either before or after starting ofatumumab treatment. 	Endpoint(s) for primary objective(s) 
 Proportion of RMS patients having established SARS-CoV-2-specific T cells as defined by detection of SARS-CoV-2 reactive T-cells, measured by e.g. enzyme-linked immunosorbent spot (ELIspot) assay from T-cells that were stimulated with SARS-CoV-2 peptide mix, either one month after second dose of vaccine or one month after booster vaccine in participants who received the respective vaccine before or after starting ofatumumab treatment (yes/no)
Secondary Objective(s) 
 To estimate the proportion of RMS patients maintaining for up to 18 months SARS-CoV-2-specific T cells after receiving a modRNA vaccine either before or after starting ofatumumab treatment. To estimate the increase in specific T-cells after receiving a modRNA booster vaccine either before or after starting ofatumumab treatment. 	Endpoint(s) for secondary objective(s) 
 Proportion of RMS patients with detectable SARS-CoV-2 reactive T-cells one week, 6, 12 and 18 months after second dose of vaccine or 6 and 12 months after booster vaccine in participants who received the vaccine before or after starting ofatumumab treatment (yes/no) Fold change of SARS-CoV-2 specific T-cell levels one week, 1 month, 6 months, 12 months and 18 months after the second dose of vaccine or 1 months, 6 months and 18 months after a booster vaccine compared to the last timepoint before the respective vaccine

Objective(s)	Endpoint(s)

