1.2 Study objectives and endpoints

Objective(s)	Endpoint(s)
Primary Objective(s) To estimate the proportion of RMS patients having established SARS-CoV-2-specific T-cells after receiving a modRNA vaccine (initial or booster) either before or after starting ofatumumab treatment.	Endpoint(s) for primary objective(s) Proportion of RMS patients having established SARS-CoV-2-specific T-cells as defined by detection of SARS-CoV-2 reactive T-cells, measured by e.g. enzyme-linked immunosorbent spot (ELIspot) assay from T-cells that were stimulated with SARS-CoV-2 peptide mix, either one month after second dose of vaccine or one month after booster vaccine in participants who received the respective vaccine before or after starting ofatumumab treatment (yes/no)
Secondary Objective(s) To estimate the proportion of RMS patients maintaining for up to 18 months SARS-CoV-2-specific T cells after receiving a modRNA vaccine either before or after starting ofatumumab treatment.	Endpoint(s) for secondary objective(s) Proportion of RMS patients with detectable SARS-CoV-2 reactive T-cells one week, 6 and 18 months after second dose of vaccine or 6 and 12 months after booster vaccine in participants who received the vaccine before or after starting ofatumumab treatment (yes/no)
To estimate the increase in specific T-cells after receiving a modRNA booster vaccine either before or after starting ofatumumab treatment.	Fold change of SARS-CoV-2 specific T-cell levels one week, 1 month, 6 months, 12 months and 18 months after the second dose of vaccine or 1 months, 6 months and 18 months after a booster vaccine compared to the last timepoint before the respective vaccine
To estimate the proportion of RMS patients achieving seroconversion (i.e. having SARS-CoV-2 serum neutralizing antibodies) after receiving a modRNA vaccine either before or after starting ofatumumab treatment.	Proportion of RMS patients achieving seroconversion (i.e. having SARS-CoV-2 serum neutralizing antibodies) after receiving a modRNA vaccine either before or after starting ofatumumab treatment (yes/no)

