To estimate the proportion of RMS patients maintaining for up to 18 months quantifiable levels of SARS-CoV-2 serum functional antibodies after receiving a modRNA vaccine either before or after starting ofatumumab treatment.	Proportion of RMS patients with quantifiable levels of SARS-CoV-2 serum functional antibodies one week, 1, 6, 12, and 18 months after receiving the second dose of modRNA vaccine or 1, 6, and 12 months after a booster shot either before or after starting ofatumumab treatment (yes/no)

Describing phenotypically the cellular response after receiving a modRNA vaccine either before or after starting ofatumumab treatment.

- Phenotypical characterization of peripheral blood mononuclear cells for CD45, CD3, CD4, CD8, CD62l, CD45RA, CD27, CCR7
- Immunophenotyping for naive, central memory, effector memory, and effector cells on CD4+ and CD8+ cells
- Measuring cells positive for intracellular cytokine-staining for interferon-gamma and interleukin-4

Describing safety and tolerability, incl. AEs, SAEs, incl. patients with clinical confirmed patients developing coronavirus disease COVID-19 2019 (COVID-19)

2 Statistical methods

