2.2 Analysis sets

For all analysis sets, participants will be analyzed according to the study treatment received.

The Safety Analysis Set (SAF) will include all participants that received any study drug.

The Efficacy Analysis Set (EAS) will include all patients of the Safety Set who received a mRNA vaccine. Patients who failed their second dose of mRNA vaccine are included in the Efficacy Analysis Set, but counted as non-responders. Patients with invalid or missing efficacy parameter at a respective time point are included in the EAS, but excluded from the denominator for that time point when calculating responder-rates.

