2.5 Analysis of the primary objective

2.5.1 Primary endpoint

The **primary clinical question** of interest is: What is the proportion of RMS patients having developed a specific immune response after receiving a modRNA vaccine (either initial vaccination or booster) either before or after starting ofatumumab treatment. The justification for the primary estimand is that it will capture whether ofatumumab-treated patients will mount

a specific T-cell response after receiving a SARS-CoV-2 mRNA vaccine assessed by enzyme-linked immunosorbent spot (ELISpot) assays from T-cells that were stimulated with SARS-CoV-2 peptide mix. Patients will receive either their initial vaccination (1st and 2nd SARS-CoV-2 vaccines) or a booster vaccine before or after starting ofatumumab treatment. In both cases we want to assess if ofatumumab initiation negatively affects or prevents the immune response.

Since this is not a randomized trial, no randomization needs to be preserved and the ITT-principle and the associated estimands framework do not apply. However, this protocol will keep as close as appropriate to the terminology and the definitions established within that framework.

The primary estimand is described by the following attributes:

1. **Population:** Patients with relapsing MS (RMS) divided in two cohorts, each receiving a SARS-CoV-2 mRNA vaccine as part of clinical routine: (1) vaccination before start of ofatumumab treatment, (2) vaccination after having been on stable ofatumumab treatment for at least 4 weeks. The SARS-CoV-2 mRNA vaccine can be either the initial vaccination cycle (for patient that are exposed to the vaccine for the first time; cohort 1a and cohort 2a) or a booster vaccination (for patients that have already completed the initial vaccination cycle; cohort 1b and cohort 2b). Patients in cohort 1a or 2a who fail to receive their second dose of vaccine for whatever reason will be included in the analysis as non-responders. Patients in cohorts 1a and 2a who did receive their second dose of vaccine and patients in cohorts 1b and 2b who received their booster shot and do not have a valid determination of specific T-cell response to SARS-CoV-2 for whatever reason will be excluded from the analysis of vaccine efficacy.

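### The secondary objective is about maintaining a response, but the planned by-visit proportions do not follow the Month 1 responders, so later gains can offset losses

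*SAP*

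**What the plan says.** **Objective.** SAP 1.2 and Protocol Table 2-1 state it as "To estimate the proportion of RMS patients maintaining for up to 18 months SARS-CoV-2-specific T cells after receiving a modRNA vaccine". A parallel objective concerns functional antibodies.

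**Endpoint.** For T cells, SAP 1.2 gives "Proportion of RMS patients with detectable SARS-CoV-2 reactive T-cells one week, 6 and 18 months after second dose of vaccine", plus Months 6 and 12 after a booster. Protocol Table 2-1 has one more visit: "Proportion of RMS patients with detectable SARS-CoV-2 reactive T-cells one week, 6, 12 and 18 months after second dose of vaccine". For antibodies, SAP 1.2 gives "Proportion of RMS patients with quantifiable levels of SARS-CoV-2 serum functional antibodies one week, 1, 6, 12, and 18 months" after the second dose, and Months 1, 6 and 12 after a booster. None of these is conditional on an earlier response.

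**Denominators.** Under SAP 2.2, patients with a missing or invalid result at a visit are "included in the EAS, but excluded from the denominator for that time point when calculating responder-rates". Patients who missed the second dose count as non-responders; Protocol 12.1 puts them in the efficacy set at every time point. SAP 2.7.3 replaces no missing values.

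**Planned displays.** SAP 2.5.4 tabulates IFN-gamma and IL-2 reactivity separately at each visit, with summary statistics and boxplots of the stimulation index. SAP 2.1 presents tables by cohort. SAP 2.7.1 lists seroconversion (Months 1, 6 and 12), phenotyping and relapse rate. It does not list the combined T-cell response of SAP 5.3.1, under which reactivity on either cytokine counts.

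**Timing in cohort 1.** Protocol section 3 starts ofatumumab at the visit four weeks after the second dose (1a) or the booster (1b), or earlier if medically indicated, but not before two weeks.

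**The concern.** Maintenance is a property of a patient: a response that was present is still present. A proportion taken afresh at each visit measures prevalence. The two agree only if nobody converts late and missing samples are unrelated to response. Neither can be assumed here, because optional boosters are allowed at any time after the second dose (Protocol section 3), infections can occur, and follow-up lasts up to 18 months.

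At stake is how the durability result is read. A steady rate could be reported as a maintained response when some patients had lost theirs and others had gained one. A change in the rate could partly reflect who was sampled.

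The point matters most in cohort 1. For most of these patients the Month 1 sample precedes ofatumumab, so what happens to an established response after treatment starts can be seen only from Month 1 onward. The fold change in SAP 1.2 does not isolate this step, because its reference is the last sample before the vaccine.

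**Working it through.** **1. The plan's own figures.** Protocol 12.8.1 and SAP 3 give n = 20 per arm, with 95% half-widths of 20.1%, 19% and 17.5% at response rates of 70%, 75% and 80%. The formula 1.96 × √(p(1−p)/20) gives 20.08%, 18.98% and 17.53%, so they reproduce. Enrolment of 22 is 20 × 1.10. These figures concern the response rate; the documents give none for maintenance.

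**2. Gains offsetting losses.** Let R be the Month 1 responders among 20, L those who lose the response and G the Month 1 non-responders who become positive. With complete data:

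- later by-visit rate = (R − L + G)/20
- maintained among Month 1 responders = (R − L)/R

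If L = G = k, the later rate equals the Month 1 rate for every k up to 20 − R. The n and the rates come from the plan; k is assumed. For R = 15 (75%):

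| k | Later rate | Maintained | Exact 95% CI |
|---|---|---|---|
| 0 | 75% | 15/15 = 100% | 78.2–100 |
| 1 | 75% | 14/15 = 93.3% | 68.1–99.8 |
| 2 | 75% | 13/15 = 86.7% | 59.5–98.3 |
| 3 | 75% | 12/15 = 80.0% | 51.9–95.7 |
| 4 | 75% | 11/15 = 73.3% | 44.9–92.2 |
| 5 | 75% | 10/15 = 66.7% | 38.4–88.2 |

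With R = 14 (70%), maintenance can fall to 8/14 = 57.1% with no visible change; with R = 16 (80%), to 12/16 = 75.0%.

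**3. Dependence on late conversion.** Assume 80% respond at Month 1 and 30% of them lose the response, so true maintenance is 70%. With a fraction c of non-responders converting, the later rate is 0.8 × 0.7 + 0.2c.

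- c = 10%: 0.56 + 0.02 = 58%, and 58/80 = 72.5% of the Month 1 rate, close to 70%.
- c = 60%: 0.56 + 0.12 = 68%, and 68/80 = 85% of the Month 1 rate, well above 70%.

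The documents give no value for c.

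**4. Shifting denominators, both directions (assumed counts).**

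- *Non-responders missing.* Start from 15/20. Four Month 1 non-responders have no later sample and three responders lose the response. The later rate is 12/16 = 75%, unchanged, while 12/15 = 80% maintained.
- *Random missingness with missed second doses.* Start from 16/20, where two non-responders missed dose 2 and stay in the denominator. One third of the other 18 are unsampled at random. The expected rate is (16 × 2/3)/(18 × 2/3 + 2) = 10.67/14 = 76%, down from 80% with no response lost. That shift is small beside the 17.5-point half-width.

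**5. What can be recovered from the planned tables.** SAP 2.5.4 gives IFN-gamma and IL-2 separately. If a patients are positive on one and b on the other out of n, the number positive on either lies anywhere from max(a, b) to min(a + b, n). The SAP 5.3.1 response at later visits therefore cannot be rebuilt from those two tables, and neither table links a patient's Month 1 result to a later one.

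**6. Month 12 after dose 2.** Protocol Table 2-1 includes it for this endpoint, and SAP 2.1.3 lists it as an efficacy visit for cohorts 1a and 2a. SAP 1.2 includes it for fold change and antibodies but omits it for detectable T cells.

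**The case against.** The strongest reply is that the SAP implements what the protocol defines. Table 2-1 specifies a by-visit proportion, Protocol 12.1 specifies visit-specific sets, and the study is purely descriptive. Conditioning on Month 1 responders is also not the only definition: response at both visits over all patients is another (in the k = 3 case, 12/20 = 60%, CI 36.1–80.9). This stands to the extent that the planned rates are legitimate and should stay. It does not make them an estimate of maintenance.

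Four stronger readings are tempting, and the documents do not support them.

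- *That cohort 1's change after starting ofatumumab is never shown.* SAP 2.5.4 with 2.1 puts cohort-level reactivity and stimulation indices side by side at every visit. What is missing is the paired, within-patient summary.
- *That no combined T-cell response is intended after Month 1.* SAP 1.2 names later rates, 2.1.3 lists the later efficacy visits, and 2.2 and 2.5.3 give denominator rules by time point. The intention is implied; SAP 2.7.1 does not state it.
- *That the step from Month 1 to Month 6 isolates an effect of ofatumumab.* The plan does want to know "In both cases we want to assess if ofatumumab initiation negatively affects or prevents the immune response". However, natural waning and boosters coincide with the start of treatment, there is no untreated group in the study, and some patients start before Month 1.
- *That the omission is proven.* The table shells are not provided and the heading between SAP 2.7.3 and 2.9 is blacked out, so an unseen paired display cannot be excluded.

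Conditioning has its own flaw. Selecting patients on one positive result from a thresholded assay, with equivocal counted as reactive (SAP 5.3.1), invites regression to the mean and some apparent loss.

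**Conclusion.** The concern holds in a limited form. The objective is about maintaining a response; the planned endpoints are unconditioned by-visit proportions with visit-specific denominators, for T cells and antibodies alike. At the planned n, an unchanged 75% is compatible with 67% to 100% maintained. That range rests on 15/20 responders, complete data and equal gains and losses. The actual distortion is unknown and can run either way; with little late conversion it nearly vanishes.

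Two smaller gaps belong with it: SAP 2.7.1 does not name the either-cytokine response at later visits, and SAP 1.2 omits Month 12 after dose 2, probably a clerical slip. All of this concerns descriptive secondary endpoints and leaves the primary Month 1 estimate untouched. The change is worth making because it answers the stated objective at little cost.

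**What to change.** Keep the by-visit rates and add the following.

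1. In SAP 2.7.1, state the SAP 5.3.1 response as an analysis at Week 1 and Months 6, 12 and 18 after the second dose, and at Months 6 and 12 after the booster for cohorts 1b and 2b. Restore Month 12 after dose 2 in SAP 1.2.
2. Per cohort, add a 2×2 table of Month 1 response by response at each later visit, with the number of Month 1 responders lacking a valid later sample.
3. Report the proportion still responding among Month 1 responders with a valid later sample, with a Clopper-Pearson 95% CI.
4. Do the same for functional antibodies, using positive or negative status at each visit, because SAP 5.3.2 leaves seroconversion underivable in patients positive at baseline.
5. Flag samples taken after an additional vaccine dose or a COVID-19 infection.
6. For cohort 1, classify each Month 1 sample as before or on ofatumumab by the actual start date, and present the later change as descriptive only.

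The cost is a few tables from data already collected. The downsides are smaller denominators, wider intervals (for example 51.9–95.7% for 12/15) and some apparent loss from selecting on a single positive result; the last should be stated beside the table.

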2.1 Data analysis general information

Data analysis will be performed by the CRO [REDACTED]. The software SAS, version 9.2 or higher is used.

Categorical data will be summarized as frequencies and percentages. According to the small sample size of this study, percentages are presented without decimal places, i.e. as integers without digits.

For continuous data, mean, standard deviation, median, minimum, and maximum will be presented.

All listings and tables will be presented by cohort.

2.1.1 General definitions

Study treatments

The modRNA vaccine and the ofatumumab treatment are defined both as study treatments. The ofatumumab treatment which is started either before or after receiving a SARS-CoV-2 mRNA vaccine (either initial or booster) is considered as treatment of interest.

Screening failure

A screening failure is a patient not eligible for the study. Screening failures are identified by:

- any inclusion criterion is violated or
- any exclusion criterion applies

2.1.2 Handling with unscheduled visits

In this study unscheduled visits may be performed for various reasons. If laboratory data (i. e. the primary and secondary parameters) are available for unscheduled visits it will be checked if the unscheduled visit replaces a scheduled visit. This will be done before analysis in the data review meeting and documented in the minutes.

2.1.3 Visits relevant for efficacy analyses

The following table shows which visits in each cohort are relevant for efficacy analysis and how they are numbered¹:

	Baseline	Week 1	Month 1	Month 6	Month 12	Month 18
Cohort 1a (Ofatumumab after initial vaccination)	Screening/ Baseline (101; 10)	Visit 1 (104; 1000)	Visit 2 (105; 1010)	Visit 7 (110; 1060)	Visit 8 (112; 1120)	Visit 9 (113; 1180)

¹ The first number indicates the visit number of raw data. This visit number deviates in the different cohorts. The second number is the visit number used in the analysis data. This number was assigned uniformly across all cohorts.

Cohort 1b (Ofatumumab after booster vaccination)	Screening (701; 10)	n.a.	Visit 1 (705; 1010)	Visit 6 (710; 1060)	Visit 7 (713; 1120)	n.a.
Cohort 2a (Ofatumumab before initial vaccination)	Baseline (Visit 4) (205, 10)	Visit 5 (208, 1000)	Visit 6 (209, 1010)	Visit 8 (213, 1060)	Visit 9 (214, 1120)	Visit 10 (215; 1180)
Cohort 2b (Ofatumumab before booster vaccination)	Baseline (808; 10)	n.a.	Visit 4 (809, 1010)	Visit 6 (811; 1060)	Visit 7 (812; 1120)	n.a.

2.2 Analysis sets

For all analysis sets, participants will be analyzed according to the study treatment received.

The Safety Analysis Set (SAF) will include all participants that received any study drug.

The Efficacy Analysis Set (EAS) will include all patients of the Safety Set who received a mRNA vaccine. Patients who failed their second dose of mRNA vaccine are included in the Efficacy Analysis Set, but counted as non-responders. Patients with invalid or missing efficacy parameter at a respective time point are included in the EAS, but excluded from the denominator for that time point when calculating responder-rates.

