2. **Variable:** Receiving the second dose of mRNA vaccine (for cohort 1a and 2a) or a booster vaccination (cohort 1b and 2b) and mounting a specific T cell response² one month after second dose of vaccine (cohort 1a and 2a) or booster vaccine (cohort 1b and 2b) defined by detection of SARS-CoV-2 specific T-cells by ELISpot assays after stimulation of T-cells with SARS-CoV-2 peptide mix (yes/no)
3. **Treatment of interest:** ofatumumab treatment, which is started either before or after receiving a SARS-CoV-2 mRNA vaccine (initial vaccination cycle or booster vaccine)
4. **Intercurrent events:**
 - a. Vaccination with a non-mRNA vaccine: patients will be excluded from the study
 - b. Failure to receive the second dose (for cohorts 1a and 2a) of vaccine: patients will be classified as non-responders
 - c. Failure to initiate ofatumumab treatment within six weeks after completion of the vaccination cycle (cohort 1a) or of the booster vaccine (cohort 1b): patients will be excluded from the efficacy analyses

² See appendix 5.3.1 for derivation

d. Failure to complete ofatumumab initiation or interruption of ofatumumab treatment prior to first vaccination (cohort 2a) or prior to booster vaccination (cohort 2b): patients will be excluded from the study

e. No valid detection of SARS-CoV-2 specific T-cells: patients will be excluded from the efficacy analyses if they received their second dose of vaccine (cohorts 1a and 2a) or booster vaccine (cohort 1b and 2b) and further analyses will be performed to confirm methodical reasons

5. **Summary measure:** n.a., there will be no formal comparison between cohorts. Response rates will only be calculated within each cohort.

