2.5.2 Statistical hypothesis, model, and method of analysis

The efficacy analysis set is used for all analyses of the primary parameter.

The primary analysis will not use any statistical testing or modelling. The absolute numbers and the proportion of participants achieving SARS-CoV-2-specific T-cell response within each cohort will be calculated. It will be augmented by a (descriptive) two-sided 95% confidence interval (exact Clopper-Pearson).

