2.5.3 Handling of missing values/censoring/discontinuations

Cohort 1a and cohort 2a: Patients who fail to receive their first dose of vaccine for whatever reason are excluded from the efficacy analysis Set(s). The number of these patients is displayed in the patient disposition table.

Patients who fail to receive their second dose of vaccine for whatever reason will be included in the analysis as non-responders. The number of these patients is displayed in the analysis table.

Patients who did receive their second dose of vaccine and do not have a valid determination of reactive T-cells to SARS-CoV-2 for whatever reason will be excluded from the analysis of vaccine efficacy at the respective time point. The number of these patients is displayed in the analysis table.

Cohort 1b and cohort 2b: Patients who fail to receive their booster vaccination for whatever reason are excluded from the efficacy analysis Sets(s). The number of these patients is displayed in the patient disposition table.

Patients who did receive their booster vaccination and do not have a valid determination of reactive T-cells to SARS-CoV-2 for whatever reason will be excluded from the analysis of vaccine efficacy at the respective time point. The number of these patients is displayed in the analysis table.

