5.4 Rule of exclusion criteria of analysis sets

Deviation ID	Description of Deviation	Exclusion in Analyses
I01	Incl. crit. no. 1 (IFC) violated	Excluded from all analysis Sets
S02	Different vaccines at first and 2 nd vaccination	Excluded from Efficacy Analysis Set

Table 2 Subject Classification

Analysis Set	PD ID that cause subjects to be excluded	Non-PD criteria that cause subjects to be excluded
SAF/Efficacy Analysis Set	NA	Not having any study treatment
Efficacy Analysis Set	NA	No mRNA vaccine administered: - Patients of cohort 1a and 2a who missed the 1 st vaccination - Patients of cohort 1b and 2b who missed the (study) booster vaccination

6 Reference

None.

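### Intercurrent events c and d of SAP 2.5.1 are not carried into the Efficacy Analysis Set, which also does not enforce cohort 2's 4-week condition

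*SAP*

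**What the plan says.** SAP 2.5.1 builds the primary estimand around when ofatumumab was given relative to vaccination.

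- **Population, cohort 2:** "vaccination after having been on stable ofatumumab treatment for at least 4 weeks". No consequence is stated for a patient who does not meet this.
- **Event c, cohort 1:** "Failure to initiate ofatumumab treatment within six weeks after completion of the vaccination cycle (cohort 1a) or of the booster vaccine (cohort 1b"). The consequence is exclusion from the efficacy analyses.
- **Event d, cohort 2:** "Failure to complete ofatumumab initiation or interruption of ofatumumab treatment prior to first vaccination (cohort 2a) or prior to booster vaccination (cohort 2b"). The consequence is exclusion from the study.

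The rules that decide who is counted are elsewhere in the SAP.

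- **SAP 2.2:** "The Efficacy Analysis Set (EAS) will include all patients of the Safety Set who received a mRNA vaccine". A missed second dose counts as non-response. A missing or invalid result leaves the denominator at that time point.
- **SAP 2.5.2:** "The efficacy analysis set is used for all analyses of the primary parameter". SAP 2.7.1 uses the same set for the secondary efficacy parameters.
- **SAP 2.5.3:** missed vaccinations and invalid assays only, for example "Patients who fail to receive their first dose of vaccine for whatever reason are excluded from the efficacy analysis Set(s").
- **SAP 5.4:** violated consent, different vaccines at first and second dose, no study treatment, and no mRNA vaccine, the last including "Patients of cohort 1b and 2b who missed the (study) booster vaccination".
- **SAP 2.1.1:** "The modRNA vaccine and the ofatumumab treatment are defined both as study treatments".

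**The concern.** The two parts of the SAP give different denominators for the same rate. A programmer working from 2.2 and 5.4 keeps every vaccinated patient with a valid result. A programmer working from 2.5.1 removes those who meet event c or d.

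The study's two questions (Protocol 4.1) are defined by ofatumumab timing. A cohort 2 patient who interrupted ofatumumab before the vaccine does not represent vaccination on stable treatment, yet would count as such. A cohort 1 patient who never starts ofatumumab would count in the Month 6, 12 and 18 rates, where exposure after vaccination is the point of interest.

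The study is open-label. If the choice of denominator is left open, it could be made after the ELISpot results are known.

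**Working it through.** **1. Each 2.5.1 condition against the set rules**

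| Condition in SAP 2.5.1 | Consequence stated there | Carried out in 2.2, 2.5.3 or 5.4? |
|---|---|---|
| a. Non-mRNA vaccine | Out of the study | At least partly (mRNA requirement; mixed-vaccine row) |
| b. No second dose | Non-responder | Yes |
| c. No ofatumumab within six weeks (cohort 1) | Out of the efficacy analyses | No |
| d. Incomplete or interrupted ofatumumab (cohort 2) | Out of the study | No |
| e. No valid T-cell result | Out of the efficacy analyses | Yes, per time point |
| At least 4 weeks on ofatumumab (cohort 2) | None stated | No |

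**2. Can such a patient reach the rate?**

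- *Event c.* The Safety Set needs any study drug, and the vaccine counts as one (SAP 2.1.1, 2.4.1). A vaccinated cohort 1 patient who never starts ofatumumab is therefore in both the Safety Set and the Efficacy Analysis Set. Protocol 3 foresees that the start may be delayed. Event c is purely an analysis exclusion, so only the set rules can apply it.
- *Event d.* Leaving the study would remove the patient only if no Month 1 sample were taken. Protocol 9.1.1 says that stopping study treatment is not withdrawal and asks such patients to keep attending where possible. Vaccination is off site (notes to Table 8-3), about a week after the baseline visit (Protocol 3). The replacement policy (Protocol 9.1.1.1) covers only patients not vaccinated within 3 months. A valid Month 1 result can therefore exist.

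**3. Timing of event c.** The protocol equates one month with 4 weeks, which is 28 days. Six weeks is 42 days. Event c is therefore settled about 42 - 28 = 14 days after the nominal primary sample.

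**4. The plan's precision figure.** Half-width = 1.96 × √(p(1-p)/20):

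- p = 0.70: 20.08 points (stated 20.1)
- p = 0.75: 18.98 points (stated 19)
- p = 0.80: 17.53 points (stated 17.5)

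The stated figures reproduce. They serve only as a yardstick here.

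**5. Effect of removing one patient.** This assumes 20 evaluable patients in a cohort. With x responders, the rate x/20 becomes (x-1)/19 if a responder is removed and x/19 if a non-responder is removed. Intervals are exact Clopper-Pearson 95%.

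| Counted | Responder removed | Non-responder removed |
|---|---|---|
| 14/20 = 70.0% (45.7–88.1) | 13/19 = 68.4% (43.4–87.4), -1.6 | 14/19 = 73.7% (48.8–90.9), +3.7 |
| 15/20 = 75.0% (50.9–91.3) | 14/19 = 73.7% (48.8–90.9), -1.3 | 15/19 = 78.9% (54.4–93.9), +3.9 |
| 16/20 = 80.0% (56.3–94.3) | 15/19 = 78.9% (54.4–93.9), -1.1 | 16/19 = 84.2% (60.4–96.6), +4.2 |

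Two patients of the same type give shifts from -3.3 points (14/20 to 12/18 = 66.7%) to +8.9 points (16/20 to 16/18 = 88.9%).

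Protocol 12.4.4 also analyses initial and booster patients separately. In an assumed subcohort of 10, one patient gives shifts from -3.3 points (7/10 to 6/9 = 66.7%) to +8.9 points (8/10 to 8/9 = 88.9%).

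**6. Partial dates.** SAP 5.1 replaces a missing day by 15. With a true start on 1 May and vaccination on 1 June, the interval is 31 days. If the day of the start is missing it becomes 15 May, and the interval becomes 17 days. That would falsely fail a 28-day check.

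**The case against.** Several points on the other side have force.

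- **Conduct rules limit event d.** The run-in lasts at least 4 weeks, with calls at weeks 1, 2 and 4 to check dosing. Eligibility uses the baseline visit, interruptions are not permitted (Protocol 6.5), and dosing is monthly. This makes event d uncommon, but the week or so between baseline and vaccination remains open. These rules do not address event c. For late starts in cohort 1, Protocol 3 asks only that the sponsor's medical advisor be contacted.
- **Event c follows the primary sample.** A late or absent start cannot change a Month 1 ELISpot that has already been taken. This stands. A reader might infer that late starters must be removed from the Month 1 rate for it to be valid. The SAP text says they are removed, but the timing gives no reason why they need to be. Amending 2.5.1 would cure the mismatch equally well.
- **The 4-week condition is not a stated exclusion.** This also stands. A reader might count it with events c and d, but 2.5.1 gives it only as a description of the population.
- **Breaches would be visible.** SAP 2.4.1 summarises the start-to-vaccination interval, and SAP 2.1 includes minimum and maximum, so an extreme value would show. SAP 2.3.1 tabulates deviations. None of this takes the patient out of the rate, and a patient who never starts has no interval to summarise.
- **The instruction is already in 2.5.1.** This is true, and it makes the defect an internal inconsistency. The set rules are still what will be programmed.

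**Conclusion.** The inconsistency is real and can be checked from the text. Events c and d of SAP 2.5.1 are not applied in the set used for the efficacy rates, and the cohort 2 population attribute of at least 4 weeks on ofatumumab is not enforced there either.

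The likely effect is small. The number affected is unknown and may be zero. Under the assumptions of 20 evaluable patients and 70–80% response, one patient moves a cohort rate by -1.6 to +4.2 points, well inside the planned half-width. The analysis is descriptive, with no test or formal comparison.

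Two stronger readings are not supported. One is that the primary rate is biased in a known direction: nothing in the documents says whether affected patients would be responders. The other is that the SAP departs from the protocol's analysis set. Protocol 12.1 omits the same exclusions, so the conflict is with the estimand in SAP 2.5.1 and its counterpart in Protocol 2.1. This is a minor correction, worth making because it is cheap.

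**What to change.** 1. **Cohort 2.** Add one row to SAP 5.4, with matching text in 2.2. It excludes from the Efficacy Analysis Set patients with incomplete initiation or interrupted ofatumumab before the first vaccination (2a) or the study booster (2b). Apply the 4-week population attribute in the same row, with any day tolerance written out. Use dose and vaccination dates only.
2. **Event c.** Choose one and write it down. Either add a 5.4 row that applies it to all efficacy analyses, as 2.5.1 now states, or amend 2.5.1 so that it applies only to the later time points (Month 6, 12 and 18). Make the choice without reference to ELISpot results.
3. **Reporting.** Keep these patients in the Safety Set and list them with dose and vaccination dates. Settle partial ofatumumab dates at the data review meeting, not by the 15/6 replacement.

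The cost is one or two rows in 5.4, a sentence in 2.2 and possibly an edit to event c. No new data are needed, since SAP 2.4.1 already uses these dates. Denominators may fall slightly and intervals widen a little.
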